4.10 Analysis Visit Windows

All by-visit summaries and analyses will use the analysis visits. Scheduled, unscheduled and early termination visits will be windowed based on the following analysis visit windows which are based on study day. Details of the analysis visit window of efficacy and safety assessments/measurements collected during clinical visits are in the table below.

Table 3 Analysis visit windows for efficacy and safety assessments or measurements collected during clinical visits

Analysis Visit	Target Study Day	CCI	Analysis Windows for ACT, PEF testing, Respiratory exam, Full physical examination, Vital signs, Blood samples for hematology and biochemistry, Urinalysis, Pregnancy test	Analysis Windows for 12-lead ECG, Pre-Dialysis and Post-Dialysis Weight	Analysis Windows for Height, Blood sample for virology and TB test, FSH	CCI
Baseline	1		≤ 1	≤ 1	≤ 1	
Week 4	29		2 to 42	NA	NA	
Week 8	57		43 to 70	NA	NA	
Week 12	85		71 to 113	≥ 2	NA	
Week 20	141		≥ 114	NA	NA	

If multiple assessments/measurements are taken within the same window, then all assessments will be listed, and the following rules will be applied for determining the values to be used for the summaries and analyses:

- Efficacy assessments: the assessment/measurement closer to the target study day will be used for the summaries and analyses. If there are multiple measurements with same difference from target day, the latest assessment will be used for the summaries and analyses.
- Safety assessments, excluding clinical laboratory tests: the assessment/measurement closer to the target study day will be used for the summaries and analyses. If there are multiple measurements with same difference from target day, the latest assessment will be used for the summaries and analyses.

- Clinical laboratory tests: the latest assessment will be used for the summaries and analyses.

CCI

Analysis visits of ePRO data will be defined depending on the data collection as below.

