12.2 Clinical Laboratory Evaluations

Clinical laboratory evaluations will be performed according to the schedule of assessments in [Appendix A](#).

The safety laboratory assessments include the following parameters:

Hematology:

- Hemoglobin (g/L)
- Hematocrit (L/L)
- White blood cell count (with differential including eosinophils) ($10^9/L$)
- Red blood cell count ($10^{12}/L$)
- Platelet count ($10^9/L$)
- Erythrocytes Mean Corpuscular Volume (fL)

Urinalysis:

- pH
- Bacteria
- Glucose
- Casts
- Crystals
- Epithelial Cells
- Erythrocytes
- Ketones
- Occult Blood
- Protein
- Leukocytes
- Leukocytes Esterase
- Mucous Threads
- Nitrites
- Bilirubin
- Urobilinogen
- Specific gravity
- Yeast Cells

Serum chemistry:

- Creatinine (umol/L)
- Aspartate Amino Transferase (AST) (U/L)
- Alanine Amino Transferase (ALT) (U/L)
- Gamma glutamyltransferase (U/L)
- Alkaline Phosphatase (U/L)
- Lactate Dehydrogenase (U/L)
- Total Bilirubin (umol/L)
- Direct Bilirubin (umol/L)
- Albumin (g/L)
- Total Protein (g/L)
- Urate (mmol/L)
- Sodium (mmol/L)
- Potassium (mmol/L)
- Calcium (mmol/L)
- Chloride (mmol/L)
- Glucose (mmol/L)
- Urea Nitrogen (mmol/L)
- Total Cholesterol (mmol/L)
- Triglycerides (mmol/L)
- Low-density lipoprotein (LDL) Cholesterol (mmol/L)

- High-density lipoprotein (HDL) Cholesterol (mmol/L)
- Creatine Kinase (CK) (U/L)

Summary statistics of the observed values and change from baseline for all laboratory parameters will be provided by visits and treatment groups.

For quantitative parameter, results will be presented for each parameter by treatment in a shift table, using above, below, within normal range, between baseline and visits at Week 4, Week 8, Week 12 and Week 20. Results will be presented for each parameter by treatment group in a shift table, using normal, abnormal not clinically significant and abnormal clinically significant categorization based on the current version of Central Lab Manual and Alert Report Specification, between baseline and visits at Week 4, Week 8, Week 12 and Week 20.

Last post-baseline and worst post-baseline results (derived using both scheduled and unscheduled measurements) will also be included in summaries and shift tables. For each parameter, worst post-baseline value will be defined as the highest or lowest value relative to the reference range.

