12.6 Vital Sign Measurements

Vital signs including pulse rate (beats/min), systolic and diastolic blood pressure (mmHg), body temperature (C), pre-dialysis weight (kg) and post-dialysis weight (kg) will be assessed over time during the study according to the schedule of assessments in [Appendix A](#). Descriptive statistics of observed values and change from baseline will be summarized by visit and by treatment.

Results from overall interpretation of vital signs assessments will be summarized by visit and treatment group and will be presented by treatment group in a shift table, using normal, abnormal not clinically significant and abnormal clinically significant categorization, between baseline and visits at Week 4, Week 8, Week 12 and Week 20.

All post-baseline (both scheduled and unscheduled) measurements will be used for Potentially Clinically Significant Values (PCSV) determination (criteria are available in [Appendix E](#)).

Number and proportions of subjects with Potentially Clinically Significant Values will be summarized by visits and treatment groups.

A corresponding listing with potentially clinically significant values (PCSV) flagged will also be provided.

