12.9 Respiratory Assessments

PEF and ACT will be performed according to subjects' asthma history as follows:

- 1) If subjects have no asthma history, PEF will be performed at Screening and Baseline.
- 2) If subjects have asthma history, PEF and ACT will be performed at all visits according to the schedule of assessments in [Appendix A](#).
- 3) If subjects have a new (de novo) diagnosis of asthma PEF and ACT will be performed at all subsequent visits (considering that some subjects will have performed some PEF testing at prior visits as per point 1).

ACT and PEF (observed values and changes from baseline) will be summarized by visit and treatment group. A corresponding listing will be also provided for both assessments.

For ACT, the numbers and percentages of subjects with an ACT score ≤ 19 will be summarized by visit and treatment group.

For PEF, the numbers and percentages of subjects with PEF $< 80\%$ of the predicted value will be presented by visit and treatment group and percent change from baseline will be classified as follows

- $\leq -20\%$
- $\leq -15\%$ and $> -20\%$
- $\leq -10\%$ and $> -15\%$
- $< 0\%$ and $> -10\%$
- $\geq 0\%$ and $< 10\%$

- $\geq 10\%$ and $< 15\%$
- $\geq 15\%$ and $< 20\%$
- $\geq 20\%$

and will be presented by visit and treatment group.

All PEF summaries will be presented for subjects with/without asthma history.

Additionally, individual plots presenting the distribution of ACT and PEF for subjects with abnormal values, over the visits will be displayed by treatment.

A listing with all known asthma triggers will be provided.

13 Independent Data Monitoring Committee

An Independent Data Monitoring Committee (IDMC) will review and monitor subject safety throughout the study. The IDMC will provide recommendations on the safety of subjects.

Details on the IDMC, including the plan of analysis for IDMC outputs, the composition of the IDMC, the procedures, roles, responsibilities, and their communications are provided in the IDMC charter.

14 Interim Analysis

No interim analysis is planned for this study.

15 Dose Selection

Dose selection will be based on the final analysis by evaluating the optimal risk-benefit and considering the potential impact of body weight.

CCI

A large black rectangular redaction box covers the majority of the page content below the 'CCI' label, starting from the 'Safety assessment' section and extending down to the page footer.

Safety assessment

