Table 14.3.4.6.2	Summary of Results of Vital Signs Evaluation	Safety Set
Table 14.3.4.6.3	Shift Tables of Results of Vital Signs Evaluation	Safety Set
Table 14.3.4.6.4	Summary of Subjects who Met Potentially Clinically Significant Value Criteria for Vital Signs	Safety Set
Table 14.3.4.7	Summary of Physical Examination	Safety Set
Table 14.3.4.8.1	Summary of Observed Value and Change from Baseline of ECG Parameters	Safety Set
Table 14.3.4.8.2	Summary of ECG Interpretation Results	Safety Set
Table 14.3.4.8.3	Shift Tables of ECG Interpretation Results	Safety Set
Table 14.3.4.9.1	Summary of Observed Value and Change from Baseline of Asthma Control Test	Safety Set
Table 14.3.4.9.2	Summary of Proportion of Subjects with Asthma Control Test Score <=19	Safety Set
Figure 14.3.4.9.3	Individual Plot of Asthma Control Test (ACT) - Subjects with Post Baseline Abnormal Values by Visit	Safety Set
Table 14.3.4.10.1	Summary of Observed Value and Change from Baseline of Percentage of Predicted PEF	Safety Set
Table 14.3.4.10.2	Summary of Classified Percent Change from Baseline of Peak Expiratory Flow Test	Safety Set
Figure 14.3.4.10.3	Individual Plot of Peak Expiratory Flow (PEF) - Subjects with Post Baseline Abnormal Values by Visit	Safety Set

TLF	Title	Analysis Set
Listing 16.2.1.1	Subjects' Disposition	Screened Set
Listing 16.2.1.2	Screen Failure/Not Assigned Subjects	Screened Set
Listing 16.2.1.3	Treatment Discontinuation	ITT Set
Listing 16.2.1.4	Study Discontinuation	ITT Set
Listing 16.2.1.5	COVID-19 Related Study Disruptions	Screened Set
Listing 16.2.2.1	Protocol Deviations	ITT Set
Listing 16.2.3.1	Inclusion/Exclusion Criteria Not Met	Screened Set
Listing 16.2.3.2	Subjects in Analysis Sets	Screened Set
Listing 16.2.4.1	Demographics and Baseline Characteristics	Screened Set
Listing 16.2.4.2	Baseline Disease Characteristics	ITT Set
Listing 16.2.4.3	Childbearing Potential Status, Methods of Contraception and Reproductive Status	Screened Set (Women only)
Listing 16.2.4.4	Medical History	ITT Set
Listing 16.2.4.5	Prior and Concomitant Medications	ITT Set
Listing 16.2.4.6	Prior and Concomitant Medical and Surgical Procedures	ITT Set
Listing 16.2.4.7	Rescue Medications	ITT Set
Listing 16.2.4.8	Rescue Medical and Surgical Procedures	ITT Set
Listing 16.2.4.9	Analysis Centers	ITT Set
Listing 16.2.4.10	Subject Scheduled Visits	ITT Set
Listing 16.2.4.11	Subject Unscheduled Visits	ITT Set
Listing 16.2.5.1	Study Drug Administration	Safety Set

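### The ACT ≤ 19 table is by visit only, so it cannot show how many subjects per arm with known asthma ever fell to that level

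*SAP*

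**What the plan says.** SAP 12.9 has ACT done at all visits in subjects with asthma history, and from diagnosis onward in de novo asthma. The threshold result is by visit: "For ACT, the numbers and percentages of subjects with an ACT score ≤ 19 will be summarized by visit and treatment group". Appendix F lists it as Table 14.3.4.9.2.

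SAP 4.10 sets the windows: "Scheduled, unscheduled and early termination visits will be windowed based on the following analysis visit windows which are based on study day". Where several values share a window, the rule is "Safety assessments, excluding clinical laboratory tests: the assessment/measurement closer to the target study day will be used for the summaries and analyses", with the latest taken if two are equally distant. The section also says that every value in a window is listed.

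For laboratory data SAP 12.2 goes further: "Last post-baseline and worst post-baseline results (derived using both scheduled and unscheduled measurements) will also be included in summaries and shift tables". SAP 12.9 has no comparable sentence for ACT. It does plan figures: "Additionally, individual plots presenting the distribution of ACT and PEF for subjects with abnormal values, over the visits will be displayed by treatment".

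**The concern.** Asthma is a named risk. Protocol 8.4 reports flares that rose with dose in an earlier atopic dermatitis study among subjects with pre-existing asthma: 1.8%, 3.6%, 12.3% and 17.5% on placebo, 10, 30 and 90 mg. This trial compares 30 mg, 60 mg and placebo, and doses are to be chosen on risk and benefit.

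Exclusion criterion 8 removes subjects with asthma history and ACT ≤ 19 at screening or baseline. In an eligible subject with known asthma, a later ACT ≤ 19 is therefore new. Under Protocol 16.10 such a score leads to referral, and an adverse event of special interest (AESI) is then reported on the investigator's judgment, with the managing physician's report considered. A per-arm count of subjects ever ≤ 19 would be a companion to those events that does not depend on that judgment.

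By-visit rows do not supply the count, for two reasons. The same subject can appear in several rows. And a low value taken between visits, perhaps at a visit for adverse-event follow-up (Protocol 13.2.2), usually loses to the scheduled value.

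**Working it through.** **One subject.** Known asthma, ACT 14 at an unscheduled visit on Day 50, ACT 22 at the Week 8 visit on Day 60. Both fall in the Week 8 window. Distances from Day 57 are |50 − 57| = 7 and |60 − 57| = 3. Day 60 is kept, and the subject counts as not ≤ 19.

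**How often this happens.**
- Windows (SAP Table 3): Days 2–42, 43–70, 71–113 and ≥ 114. The last is closed at Day 146 (141 + 5) by assumption.
- Scheduled visits (SAP Appendix A): Days 29 and 57 ± 3, Days 85 and 141 ± 5.
- Further assumptions: the scheduled ACT was done in its visit window, and there is one unscheduled value on another day of the same analysis window.

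For each permitted scheduled day, count the other days on which an unscheduled value would be kept. For Week 4, scheduled Days 26 to 32 give 6, 4, 2, 0, 1, 3 and 5; the mean is 21/7 = 3.

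| Visit | Other days in window | Days kept, range | Mean | Mean share |
|---|---|---|---|---|
| Week 4 | 40 | 0–6 | 3 | 7.5% |
| Week 8 | 27 | 0–6 | 3 | 11.1% |
| Week 12 | 42 | 0–10 | 5 | 11.9% |
| Week 20 | 32 | 0–10 | 5 | 15.6% |
| All | 141 | 0–32 | 16 | 11.3% |

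If unscheduled days are evenly spread (assumption), 16/141 = 11.3% of unscheduled values are kept and about 89% are not. The extremes are 0/141 (every scheduled visit on its target day) and 32/141 = 22.7%. An unscheduled value can be kept only on Days 27–32, 55–60, 81–90 and 137–146, which is 6 + 6 + 10 + 10 = 32 of 145 days. Closing the last window at Day 153 gives 16/148 = 10.8%.

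**If scheduled values are missing.** With a share m missing, the share kept is m + (1 − m) × 0.1135:
- m = 0.10: 20.2%
- m = 0.30: 37.9%

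**What by-visit counts can give.** Let n₄, n₈, n₁₂ and n₂₀ be the numbers ≤ 19 at each visit. The number of subjects ever ≤ 19 among tabulated values lies between the largest of these and the smaller of their sum and the number of subjects with ACT data. Counts of 2, 2, 2, 2 could be anything from 2 to 8 subjects. Values not selected can only raise the true number.

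**Subjects involved.** The documents give no number with asthma. Assume 5% to 10% of 84 per arm: 4.2 to 8.4 subjects. Assume a 10% chance of ACT ≤ 19 at each of 4 visits. The any-time rate then runs from 0.10 (full within-subject correlation) to 1 − 0.9⁴ = 0.344 (independence).
- 5% with asthma: 0.42 to 1.44 subjects per arm
- 10% with asthma: 0.84 to 2.89 subjects per arm

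**The case against.** The case against is strong on consequence. Every ACT value is listed (Listing 16.2.8.10), so with so few subjects the count can be made by hand. Figure 14.3.4.9.3, "Individual Plot of Asthma Control Test (ACT) - Subjects with Post Baseline Abnormal Values by Visit", comes close to naming the subjects wanted. Protocol 19.4.7 promised only a listing for ACT, so the SAP already exceeds it. An ACT ≤ 19 leads to referral whichever value the table keeps. Asthma AESIs and events adjudicated by the independent adjudication committee are tabulated without reference to ACT windows. Protocol 13.2.2 limits the reasons for unscheduled visits, and the schedule footnotes are redacted, so the number of unscheduled ACTs is unknown and could be zero. All of this stands, and it keeps the point minor. It does not give a planned per-arm count, and the SAP does not say whether the individual plots include values that were not selected.

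Three stronger readings are tempting, and the documents do not support them.
- **Vital signs as a precedent.** SAP 12.6 says "All post-baseline (both scheduled and unscheduled) measurements will be used for Potentially Clinically Significant Values (PCSV) determination", but the resulting counts are then given by visit. Only the laboratory section states a worst post-baseline row.
- **The table title as proof.** "Summary of Proportion of Subjects with Asthma Control Test Score <=19" names no any-time row, but the laboratory table titles name no worst row either, although SAP 12.2 requires one. The table shells are a separate document. The point rests on the silence of SAP 12.9 alone.
- **The same gap for peak expiratory flow.** Protocol 16.8.4 calls it only supplemental. Protocol 16.8.3 prefers it after or late in dialysis and with asthma medication withheld. A worst value from an unscheduled visit could reflect fluid status or medication timing, so a worst-value row could mislead.

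**Conclusion.** The point holds for ACT, as an optional improvement to a supporting safety table. Under the stated rules, and provided the scheduled ACT is present, most unscheduled ACT values in known asthma would not reach the ≤ 19 table: about 89% if unscheduled days are evenly spread, and 77% to 100% across the permitted scheduled days. Subjects ever ≤ 19 cannot be counted from that table even if no unscheduled value exists.

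A reader might infer that an asthma signal would be hidden, or that 89% of some known body of data is lost. Neither follows. The event tables do not use the selection rule, and the percentage applies to an unknown number of measurements. The subject numbers rest on assumed asthma prevalence and ACT rates. Efficacy and alpha are not touched.

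**What to change.** In SAP 12.9 and Table 14.3.4.9.2, add one row per arm for subjects with any post-baseline ACT ≤ 19, using all scheduled and unscheduled values as SAP 12.2 does for worst laboratory results.
- **Denominator:** subjects with asthma history at baseline and at least one post-baseline ACT.
- **De novo asthma:** show separately. These subjects have ACT only from diagnosis, so pooling them would add outcome-selected subjects to the denominator.
- **Measurements:** display the number of ACT measurements per arm.
- **Unchanged:** keep the by-visit rows, and add no worst-value rows for peak expiratory flow.
- **Plots:** have the individual ACT plots show all values, including unscheduled ones.

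The cost is one or two sentences and a few table rows from data already collected. The downside is that the chance of at least one low score rises with the number of measurements, so an arm with more unscheduled visits can look worse. The displayed measurement count lets readers judge that.

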19.1 Appendix A: Schedule of Study Procedures

Study period	Screening period ^a	Treatment period				Follow-up	Unscheduled visit ^c
Visit	V1	V2	V3	V4	V5	V6	(if applicable)
Week	W-4	Baseline	W4	W8	W12/ET ^b	W20	
Day		Day 1	Day 29	Day 57	Day 85	Day 141	
Visit window			± 3 days	± 3 days	± 5 days	±5 days	
Informed consent form	X						
Inclusion/exclusion criteria	X	X					
Demographics	X						
Baseline characteristics ^d	X	X					
Medical history, previous therapies and procedures, smoking status	X						
SUBJECT-REPORTED OUTCOME (SRO) ASSESSMENTS							
(eDiary) Daily WI NRS/SD NRS ^{e,f}	X -----					X	(X)
CCI							
SAFETY ASSESSMENTS							
ACT ^{g,i}	X	X	X	X	X	X	(X)
PEF testing ^{j,k}	X	X	X	X	X	X	(X)
Respiratory exam ^{k,l}	X	X	X	X	X	X	(X)
Full physical examination	X	X	X	X	X	X	(X)

[figure not shown]
Study period	Screening period ^a	Treatment period				Follow-up	Unscheduled visit ^c
Visit	V1	V2	V3	V4	V5	V6	(if applicable)
Week	W-4	Baseline	W4	W8	W12/ET ^b	W20	
Day		Day 1	Day 29	Day 57	Day 85	Day 141	
			± 3 days	± 3 days	± 5 days	±5 days	
Height	X						(X)
Pre-Dialysis and Post-Dialysis Weight	X	X			X		(X)
12-lead ECG ^{k,m}	X				X		(X)
Vital signs ⁿ	X	X	X	X	X	X	(X)
Contraceptive counseling	X						(X)
Adverse Events	X	X	X	X	X	X	(X)
Concomitant therapies and procedures	X	X	X	X	X	X	(X)
LABORATORY ASSESSMENTS							
Blood sample for virology (HIV, Hepatitis B, and C test)	X						(X)
Blood samples for TB test	X						(X)
Blood samples for hematology and biochemistry ^o	X	X	X	X	X	X	(X)
Urinalysis ^p	X	X	X	X	X	X	(X)
Pregnancy test ^q	X	X	X	X	X	X	(X)
FSH ^r	X						
CCI							

Study period	Screening period ^a	Treatment period				Follow-up	Unscheduled visit ^c
		V1	V2	V3	V4	V5	
Visit	V1	V2	V3	V4	V5	V6	
Week	W-4	Baseline	W4	W8	W12/ET ^b	W20	
Day		Day 1	Day 29	Day 57	Day 85	Day 141	(if applicable)
Visit window			± 3 days	± 3 days	± 5 days	±5 days	

[figure not shown]
RANDOMIZATION and STUDY DRUG ADMINISTRATION

Randomization		X					
Study drug injection and training ^{t,u,v}		X	X	X			(X)

[figure not shown]
CCI

[figure not shown]
CCI

[figure not shown]
CCI

[figure not shown]
CCI

[figure not shown]
CCI

[figure not shown]
CCI

CCI

CCI

CCI

CCI

19.6 Appendix F: List of Tables, Figures and Listings

TLF	Title	Analysis Set
Table 14.1.1.1	Summary of Subjects' Disposition	Screened Set
Table 14.1.1.2	Summary of Screen Failure/Not Assigned Subjects	Screened Set
Table 14.1.1.3	Summary of Inclusion/Exclusion Criteria Not Met	Screened Set
Table 14.1.1.4	Summary of Analysis Sets	ITT Set
Table 14.1.1.5	Summary of Subjects Accounting by Clinical Visit	ITT Set
Table 14.1.1.6	Summary of Subjects Accounting by Analysis Visit	ITT Set
Table 14.1.2.1.1	Summary of Demographics and Baseline Characteristics	ITT Set
Table 14.1.2.1.2	Summary of Demographics and Baseline Characteristics	Safety Set
CCI		
Table 14.1.2.2.1	Summary of Baseline Disease Characteristics	ITT Set
Table 14.1.2.2.2	Summary of Baseline Disease Characteristics	Safety Set
CCI		
Table 14.1.2.3	Summary of Childbearing Potential Status, Methods of Contraception and Reproductive Status	ITT Set (Women only)
Table 14.1.3.1	Summary of Major Protocol Deviations	ITT Set
Table 14.1.3.2	Summary of Major Protocol Deviations Leading to the Exclusion from PP Set	ITT Set
Table 14.1.4.1	Summary of Extent of Exposure and Compliance	Safety Set
Table 14.1.5.1	Summary of Medical History	ITT Set
Table 14.1.6.1	Summary of Prior Medications	ITT Set
Table 14.1.6.2	Summary of Concomitant Medications	ITT Set
Table 14.1.7.1	Summary of Prior Medical and Surgical Procedures	ITT Set
Table 14.1.7.2	Summary of Concomitant Medical and Surgical Procedures	ITT Set
Table 14.1.8.1	Summary of Rescue Medications	ITT Set
Table 14.1.8.2	Summary of Rescue Medical and Surgical Procedures	ITT Set
Table 14.1.8.3	Kaplan-Meier Analysis of Time to First Rescue Therapy	ITT Set
Figure 14.1.8.4	Kaplan-Meier Plots of Time to First Rescue Therapy	ITT Set
Table 14.2.1.1	Summary of Proportion of Subjects with Improvement of WI NRS ≥ 4 from Baseline - Observed Case	ITT Set
Table 14.2.1.2.1	Subgroup Summary by Age of Proportion of Subjects with Improvement of WI NRS ≥ 4 from Baseline - Observed Case	ITT Set
Table 14.2.1.2.2	Subgroup Summary by Sex of Proportion of Subjects with Improvement of WI NRS ≥ 4 from Baseline - Observed Case	ITT Set
Table 14.2.1.2.3	Subgroup Summary by Race of Proportion of Subjects with Improvement of WI NRS ≥ 4 from Baseline - Observed Case	ITT Set
Table 14.2.1.2.4	Subgroup Summary by Region of Proportion of Subjects with Improvement of WI NRS ≥ 4 from Baseline - Observed Case	ITT Set
Table 14.2.1.2.5	Subgroup Summary by Severity of Pruritus of Proportion of Subjects with Improvement of WI NRS ≥ 4 from Baseline - Observed Case	ITT Set
Table 14.2.1.2.6	Subgroup Summary by Duration of Pruritus of Proportion of Subjects with Improvement of WI NRS ≥ 4 from Baseline - Observed Case	ITT Set
Table 14.2.1.2.7	Subgroup Summary by Duration of Hemodialysis of Proportion of Subjects with Improvement of WI NRS ≥ 4 from Baseline - Observed Case	ITT Set
Table 14.2.1.2.8	Subgroup Summary by Systemic Anti-Pruritus Treatment of Proportion of Subjects with Improvement of WI NRS ≥ 4 from Baseline - Observed Case	ITT Set
Table 14.2.1.3.1	Primary Analysis (Estimand 1) - Difference in Proportions of Subjects with Improvement of WI NRS ≥ 4 from Baseline at	ITT Set

TLF	Title	Analysis Set
	Week 12 without Use of Rescue Therapies and without Treatment Discontinuation due to Lack of Efficacy or AE/Death related to the Study Drug - MI under MAR	
Figure 14.2.1.3.2	Primary Analysis (Estimand 1) - Bar Chart of Proportions of Subjects with Improvement of WI NRS ≥ 4 from Baseline at Week 12 without Use of Rescue Therapies and without Treatment Discontinuation due to Lack of Efficacy or AE/Death related to the Study Drug - MI under MAR	ITT Set
Table 14.2.1.4.1	Sensitivity Analysis 1 (Estimand 1) - Difference in Proportions of Subjects with Improvement of WI NRS ≥ 4 from Baseline at Week 12 without Use of Rescue Therapies and without Treatment Discontinuation due to Lack of Efficacy or AE/Death related to the Study Drug - MI using Copy Reference under MNAR	ITT Set
Table 14.2.1.4.2	Sensitivity Analysis 2 (Estimand 1) - Difference in Proportions of Subjects with Improvement of WI NRS ≥ 4 from Baseline at Week 12 without Use of Rescue Therapies and without Treatment Discontinuation due to Lack of Efficacy or AE/Death related to the Study Drug - Non-responder Imputation	ITT Set
Table 14.2.1.4.3	Sensitivity Analysis 3 (Estimand 1) - Difference in Proportions of Subjects with Improvement of WI NRS ≥ 4 from Baseline at Week 12 without Use of Rescue Therapies and without Treatment Discontinuation due to Lack of Efficacy or AE/Death related to the Study Drug - Tipping Point Analysis based on Delta-adjustment MI under MNAR	ITT Set
Figure 14.2.1.4.4	Sensitivity Analysis 3 (Estimand 1) - Heatmap Display of Difference in Proportions of Subjects with Improvement of WI NRS ≥ 4 from Baseline at Week 12 without Use of Rescue Therapies and without Treatment Discontinuation due to Lack of Efficacy or AE/Death related to the Study Drug - Tipping Point Analysis based on Delta-adjustment MI under MNAR	ITT Set
Table 14.2.1.4.5	Sensitivity Analysis 4 (Estimand 1) - Difference in Proportions of Subjects with Improvement of WI NRS ≥ 4 from Baseline at Week 12 without Use of Rescue Therapies and without Treatment Discontinuation due to Lack of Efficacy or AE/Death related to the Study Drug - MI under MAR (Using Weekly Averages of WI NRS Obtained by Averaging at least 3 Daily Scores over a 7-day Period)	ITT Set
Table 14.2.1.4.6	Sensitivity Analysis 5 (Estimand 1) - Difference in Proportions of Subjects with Improvement of WI NRS ≥ 4 from Baseline at Week 12 without Use of Rescue Therapies and without Treatment Discontinuation due to Lack of Efficacy or AE/Death related to the Study Drug - MI under MAR (Using Weekly Averages of WI NRS Obtained by Averaging at least 2 Daily Scores over a 7-day Period)	ITT Set
Table 14.2.1.4.7	Sensitivity Analysis 6 (Estimand 1) - Difference in Proportions of Subjects with Improvement of WI NRS ≥ 4 from Baseline at Week 12 without Use of Rescue Therapies and without Treatment Discontinuation due to Lack of Efficacy or AE/Death related to the Study Drug - MI under MAR (Using Weekly Averages of WI NRS Obtained by Averaging at least 1 Daily Score over a 7-day Period)	ITT Set
Table 14.2.1.4.8	Supplementary Analysis 1 (Estimand 1) - Difference in Proportions of Subjects with Improvement of WI NRS ≥ 4 from Baseline at Week 12 without Use of Rescue Therapies and	miTT Set

TLF	Title	Analysis Set
	without Treatment Discontinuation due to Lack of Efficacy or AE/Death related to the Study Drug - MI under MAR	
Table 14.2.1.4.9	Supplementary Analysis 2 (Estimand 1) - Difference in Proportions of Subjects with Improvement of WI NRS ≥ 4 from Baseline at Week 12 without Use of Rescue Therapies and without Treatment Discontinuation due to Lack of Efficacy or AE/Death related to the Study Drug	PP Set
Table 14.2.1.4.10	Supplementary Analysis 3 (Treatment Policy Adaptation of Estimand 1) - Difference in Proportions of Subjects with Improvement of WI NRS ≥ 4 from Baseline at Week 12 Irrespective of Use of Rescue Therapies and Treatment Discontinuation - Observed Case	ITT Set
Table 14.2.1.4.11	COVID-19 Impact (Estimand 1) - Difference in Proportions of Subjects with Improvement of WI NRS ≥ 4 from Baseline at Week 12 without Use of Rescue Therapies and without Treatment Discontinuation due to Lack of Efficacy or AE/Death related to the Study Drug - MI under MAR	ITT Set excluding Subjects with COVID-19 disruptions
Table 14.2.1.5.1	Subgroup Analysis by Age (Estimand 1) - Difference in Proportions of Subjects with Improvement of WI NRS ≥ 4 from Baseline at Week 12 without Use of Rescue Therapies and without Treatment Discontinuation due to Lack of Efficacy or AE/Death related to the Study Drug - MI under MAR	ITT Set
Table 14.2.1.5.2	Subgroup Analysis by Sex (Estimand 1) - Difference in Proportions of Subjects with Improvement of WI NRS ≥ 4 from Baseline at Week 12 without Use of Rescue Therapies and without Treatment Discontinuation due to Lack of Efficacy or AE/Death related to the Study Drug - MI under MAR	ITT Set
Table 14.2.1.5.3	Subgroup Analysis by Race (Estimand 1) - Difference in Proportions of Subjects with Improvement of WI NRS ≥ 4 from Baseline at Week 12 without Use of Rescue Therapies and without Treatment Discontinuation due to Lack of Efficacy or AE/Death related to the Study Drug - MI under MAR	ITT Set
Table 14.2.1.5.4	Subgroup Analysis by Region (Estimand 1) - Difference in Proportions of Subjects with Improvement of WI NRS ≥ 4 from Baseline at Week 12 without Use of Rescue Therapies and without Treatment Discontinuation due to Lack of Efficacy or AE/Death related to the Study Drug - MI under MAR	ITT Set
Table 14.2.1.5.5	Subgroup Analysis by Severity of Pruritus (Estimand 1) - Difference in Proportions of Subjects with Improvement of WI NRS ≥ 4 from Baseline at Week 12 without Use of Rescue Therapies and without Treatment Discontinuation due to Lack of Efficacy or AE/Death related to the Study Drug - MI under MAR	ITT Set
Table 14.2.1.5.6	Subgroup Analysis by Duration of Pruritus (Estimand 1) - Difference in Proportions of Subjects with Improvement of WI NRS ≥ 4 from Baseline at Week 12 without Use of Rescue Therapies and without Treatment Discontinuation due to Lack of Efficacy or AE/Death related to the Study Drug - MI under MAR	ITT Set
Table 14.2.1.5.7	Subgroup Analysis by Duration of Hemodialysis (Estimand 1) - Difference in Proportions of Subjects with Improvement of WI NRS ≥ 4 from Baseline at Week 12 without Use of Rescue Therapies and without Treatment Discontinuation due to Lack of Efficacy or AE/Death related to the Study Drug - MI under MAR	ITT Set
Table 14.2.1.5.8	Subgroup Analysis by Systemic Anti-Pruritus Treatment (Estimand 1) - Difference in Proportions of Subjects with Improvement of WI NRS ≥ 4 from Baseline at Week 12 without	ITT Set

TLF	Title	Analysis Set
	Use of Rescue Therapies and without Treatment Discontinuation due to Lack of Efficacy or AE/Death related to the Study Drug - MI under MAR	
Figure 14.2.1.5.9	Forest Plot (Estimand 1) - Difference in Proportions of Subjects with Improvement of WI NRS ≥ 4 from Baseline at Week 12 without Use of Rescue Therapies and without Treatment Discontinuation due to Lack of Efficacy or AE/Death related to the Study Drug - MI under MAR	ITT Set
Table 14.2.2.1	Summary of Proportion of Subjects with Improvement of WI NRS ≥ 3 from Baseline - Observed Case	ITT Set
Table 14.2.2.2.1	Subgroup Summary by Age of Proportion of Subjects with Improvement of WI NRS ≥ 3 from Baseline - Observed Case	ITT Set
Table 14.2.2.2.2	Subgroup Summary by Sex of Proportion of Subjects with Improvement of WI NRS ≥ 3 from Baseline - Observed Case	ITT Set
Table 14.2.2.2.3	Subgroup Summary by Race of Proportion of Subjects with Improvement of WI NRS ≥ 3 from Baseline - Observed Case	ITT Set
Table 14.2.2.2.4	Subgroup Summary by Region of Proportion of Subjects with Improvement of WI NRS ≥ 3 from Baseline - Observed Case	ITT Set
Table 14.2.2.2.5	Subgroup Summary by Severity of Pruritus of Proportion of Subjects with Improvement of WI NRS ≥ 3 from Baseline - Observed Case	ITT Set
Table 14.2.2.2.6	Subgroup Summary by Duration of Pruritus of Proportion of Subjects with Improvement of WI NRS ≥ 3 from Baseline - Observed Case	ITT Set
Table 14.2.2.2.7	Subgroup Summary by Duration of Hemodialysis of Proportion of Subjects with Improvement of WI NRS ≥ 3 from Baseline - Observed Case	ITT Set
Table 14.2.2.2.8	Subgroup Summary by Systemic Anti-Pruritus Treatment of Proportion of Subjects with Improvement of WI NRS ≥ 3 from Baseline - Observed Case	ITT Set
Table 14.2.2.3.1	Main Analysis (Estimand 2) - Difference in Proportions of Subjects with Improvement of WI NRS ≥ 3 from Baseline at Week 12 without Use of Rescue Therapies and without Treatment Discontinuation due to Lack of Efficacy or AE/Death related to the Study Drug - MI under MAR	ITT Set
Figure 14.2.2.3.2	Main Analysis (Estimand 2) - Bar Chart of Proportions of Subjects with Improvement of WI NRS ≥ 3 from Baseline at Week 12 without Use of Rescue Therapies and without Treatment Discontinuation due to Lack of Efficacy or AE/Death related to the Study Drug - MI under MAR	ITT Set
Table 14.2.2.4.1	Sensitivity Analysis 1 (Estimand 2) - Difference in Proportions of Subjects with Improvement of WI NRS ≥ 3 from Baseline at Week 12 without Use of Rescue Therapies and without Treatment Discontinuation due to Lack of Efficacy or AE/Death related to the Study Drug - MI using Copy Reference under MNAR	ITT Set
Table 14.2.2.4.2	Sensitivity Analysis 2 (Estimand 2) - Difference in Proportions of Subjects with Improvement of WI NRS ≥ 3 from Baseline at Week 12 without Use of Rescue Therapies and without Treatment Discontinuation due to Lack of Efficacy or AE/Death related to the Study Drug - Non-responder Imputation	ITT Set
Table 14.2.2.4.3	COVID-19 Impact (Estimand 2) - Difference in Proportions of Subjects with Improvement of WI NRS ≥ 3 from Baseline at Week 12 without Use of Rescue Therapies and without Treatment Discontinuation due to Lack of Efficacy or AE/Death related to the Study Drug - MI under MAR	ITT Set excluding Subjects with COVID-19 disruptions

TLF	Title	Analysis Set
Table 14.2.2.5.1	Subgroup Analysis by Age (Estimand 2) - Difference in Proportions of Subjects with Improvement of WI NRS ≥ 3 from Baseline at Week 12 without Use of Rescue Therapies and without Treatment Discontinuation due to Lack of Efficacy or AE/Death related to the Study Drug - MI under MAR	ITT Set
Table 14.2.2.5.2	Subgroup Analysis by Sex (Estimand 2) - Difference in Proportions of Subjects with Improvement of WI NRS ≥ 3 from Baseline at Week 12 without Use of Rescue Therapies and without Treatment Discontinuation due to Lack of Efficacy or AE/Death related to the Study Drug - MI under MAR	ITT Set
Table 14.2.2.5.3	Subgroup Analysis by Race (Estimand 2) - Difference in Proportions of Subjects with Improvement of WI NRS ≥ 3 from Baseline at Week 12 without Use of Rescue Therapies and without Treatment Discontinuation due to Lack of Efficacy or AE/Death related to the Study Drug - MI under MAR	ITT Set
Table 14.2.2.5.4	Subgroup Analysis by Region (Estimand 2) - Difference in Proportions of Subjects with Improvement of WI NRS ≥ 3 from Baseline at Week 12 without Use of Rescue Therapies and without Treatment Discontinuation due to Lack of Efficacy or AE/Death related to the Study Drug - MI under MAR	ITT Set
Table 14.2.2.5.5	Subgroup Analysis by Severity of Pruritus (Estimand 2) - Difference in Proportions of Subjects with Improvement of WI NRS ≥ 3 from Baseline at Week 12 without Use of Rescue Therapies and without Treatment Discontinuation due to Lack of Efficacy or AE/Death related to the Study Drug - MI under MAR	ITT Set
Table 14.2.2.5.6	Subgroup Analysis by Duration of Pruritus (Estimand 2) - Difference in Proportions of Subjects with Improvement of WI NRS ≥ 3 from Baseline at Week 12 without Use of Rescue Therapies and without Treatment Discontinuation due to Lack of Efficacy or AE/Death related to the Study Drug - MI under MAR	ITT Set
Table 14.2.2.5.7	Subgroup Analysis by Duration of Hemodialysis (Estimand 2) - Difference in Proportions of Subjects with Improvement of WI NRS ≥ 3 from Baseline at Week 12 without Use of Rescue Therapies and without Treatment Discontinuation due to Lack of Efficacy or AE/Death related to the Study Drug - MI under MAR	ITT Set
Table 14.2.2.5.8	Subgroup Analysis by Systemic Anti-Pruritus Treatment (Estimand 2) - Difference in Proportions of Subjects with Improvement of WI NRS ≥ 3 from Baseline at Week 12 without Use of Rescue Therapies and without Treatment Discontinuation due to Lack of Efficacy or AE/Death related to the Study Drug - MI under MAR	ITT Set
Figure 14.2.2.5.9	Forest Plot (Estimand 2) Difference in Proportions of Subjects achieving an Improvement of WI NRS ≥ 3 from Baseline at Week 12 without Use of Rescue Therapies and without Treatment Discontinuation due to Lack of Efficacy or AE/Death related to the Study Drug - MI under MAR	ITT Set
Table 14.2.3.1.1	Main Analysis (Estimand 3) - Difference in Proportions of Subjects with Improvement of WI NRS ≥ 4 from Baseline at Week 4 without Use of Rescue Therapies and without Treatment Discontinuation due to Lack of Efficacy or AE/Death related to the Study Drug - MI under MAR	ITT Set
Figure 14.2.3.1.2	Main Analysis (Estimand 3) - Bar Chart of Proportions of Subjects with Improvement of WI NRS ≥ 4 from Baseline at Week 4 without Use of Rescue Therapies and without Treatment	ITT Set

TLF	Title	Analysis Set
	Discontinuation due to Lack of Efficacy or AE/Death related to the Study Drug - MI under MAR	
Table 14.2.3.2.1	Sensitivity Analysis 1 (Estimand 3) - Difference in Proportions of Subjects with Improvement of WI NRS ≥ 4 from Baseline at Week 4 without Use of Rescue Therapies and without Treatment Discontinuation due to Lack of Efficacy or AE/Death related to the Study Drug - MI using Copy Reference under MNAR	ITT Set
Table 14.2.3.2.2	Sensitivity Analysis 2 (Estimand 3) - Difference in Proportions of Subjects with Improvement of WI NRS ≥ 4 from Baseline at Week 4 without Use of Rescue Therapies and without Treatment Discontinuation due to Lack of Efficacy or AE/Death related to the Study Drug - Non-responder Imputation	ITT Set
Table 14.2.3.2.3	COVID-19 Impact (Estimand 3) - Difference in Proportions of Subjects with Improvement of WI NRS ≥ 4 from Baseline at Week 4 without Use of Rescue Therapies and without Treatment Discontinuation due to Lack of Efficacy or AE/Death related to the Study Drug - MI under MAR	ITT Set excluding Subjects with COVID-19 disruptions
Table 14.2.3.3.1	Subgroup Analysis by Age (Estimand 3) - Difference in Proportions of Subjects with Improvement of WI NRS ≥ 4 from Baseline at Week 4 without Use of Rescue Therapies and without Treatment Discontinuation due to Lack of Efficacy or AE/Death related to the Study Drug - MI under MAR	ITT Set
Table 14.2.3.3.2	Subgroup Analysis by Sex (Estimand 3) - Difference in Proportions of Subjects with Improvement of WI NRS ≥ 4 from Baseline at Week 4 without Use of Rescue Therapies and without Treatment Discontinuation due to Lack of Efficacy or AE/Death related to the Study Drug - MI under MAR	ITT Set
